Sponsor	DermBiont Inc.
TEAEs	Treatment-emergent Adverse Events
Telemedicine	An audiovisual communication that remotely connects investigators at site with subjects at home

SYNOPSIS

NAME OF SPONSOR: DermBiont Inc.		
NAME OF FIN	NAME OF FINISHED PRODUCT: DBI-001	
NAME OF AC	TIVE INGREDIENT(S):	
Title of Study	A Randomized, Observer-blinded, Within Subject Bilateral Comparison to Study the Safety and Efficacy of Daily Application for 4 weeks of DBI- 001 Gel Vs. Aqueous Gel in Subjects with Atopic Dermatitis	
Investigator(s)	TBD	
Study centre(s)	Multiple centres	
Publication	N/A	
Phase of development	Phase 2b	
Objectives	Primary Objective:	
	• Effect of daily application of DBI-001 on the signs and symptoms of atopic dermatitis (AD).	
	 Secondary Objectives: Determine the antibacterial effect of daily applications of DBI-001 on the abundance of S. aureus in the cutaneous microbiome. To determine the safety and tolerability of DBI-001 Gel vs. Aqueous Gel in subjects with AD. Evaluation of the presence and persistence of strain following daily applications of DBI-001 for 4 weeks. Characterize changes in abundance and diversity of the microbiome during and following 4 weeks of daily applications of DBI-001. Mathematical Section (Section 1997) Determine (Section 2007) Defense (Section 2007) Determine (Section 2007) Determin	

Study Design and Evaluation Methods	 A randomized, Observer-blinded, daily application, bilateral study of DBI-001 Gel vs. Aqueous Gel in subjects with AD. Approximately 20 subjects will be enrolled with clinically stable AD according to the criteria of Hanifin and Rajka¹ with comparable anatomically symmetrical, bilateral target lesions (Hanifin and Rajka 1980). Subjects meeting the inclusion/exclusion criteria will be enrolled into the study. Subjects will be instructed to adhere to treatment site restrictions to avoid specific activities 12 hrs. prior to clinic visits and 12 hrs. after test article application that could adversely impact the quality of samples or remove the test articles from the treated sites. Showering or rinsing with water is acceptable. Each subject will have 1 site identified on comparable anatomically symmetrical, bilateral areas spanning approximately 100 cm², which is approximately the area of the palm of the hand. Clinical evaluations of two sites of AD will be done by an evaluating investigator(s) who is blinded to treatment assignments. The Atopic Dermatitis Severity Index (ADSI) (Van Leent et al. 1998) is the sum of the severity scores of the signs and symptoms of AD including erythema, pruritus, exudation, excoriation and lichenification. At Baseline (prior to test article application) and then at, Day 7 (±2),14 (±2), 21 (±2), 28 (±2), 35 (±4) and 42 (±4), samples will be collected using PBS swabs for microbiologic evaluation from both treatment sites. Both treated sites on all subjects will be treated with 27 daily doses (once daily application for 4 weeks) of the assigned test articles applied by study personnel at the baseline visit, Days 7 (±2),14 (±2), and 21 (±2). Between visits on weekdays, subjects, or legally authorized representative (LAR), will apply the daily doses during telemedicine visits with a treating investigator, or qualified delegate. On weekends subjects or LAR will apply doses
Methodology	Observer-Blinded, Randomized, Aqueous Gel-Controlled, Bilateral
Number of subjects	Approximately 20 Subjects
Study Population	Males and females ages 12-65, in general good health with AD and comparable anatomically symmetrical bilateral AD lesions areas.

 Criteria 1. Ability to understand, agree to, and sign the study Informed Consent. If the subject is unable to provide consent for him/herselin the subject's legally authorized representative may provide writter consent. 2. A signed Health Information Portability and Accountability Act (HIPAA) authorization form which permits the use and disclosure 	f, n
 Consent. If the subject is unable to provide consent for him/hersel: the subject's legally authorized representative may provide writter consent. A signed Health Information Portability and Accountability Act (HIPAA) authorization form which permits the use and disclosure 	f, n
 the subject's legally authorized representative may provide writter consent. A signed Health Information Portability and Accountability Act (HIPAA) authorization form which permits the use and disclosure 	, 1
 a subject s legarly authorized representative may provide writer consent. A signed Health Information Portability and Accountability Act (HIPAA) authorization form which permits the use and disclosure 	,
 2. A signed Health Information Portability and Accountability Act (HIPAA) authorization form which permits the use and disclosure 	l ,
(HIPAA) authorization form which permits the use and disclosure	l,
(HIPAA) authorization form which permits the use and disclosure	l,
	l,
of subject's individually identifiable health information.	l,
3. Male or Female Subjects of any race 12-65 years of age.	l,
4. Physician diagnosed clinically stable AD according to the criteria	l,
of Hanifin and Rajka ⁿ with comparable anatomically symmetrical	
bilateral target lesions (Hanifin and Rajka 1980). Lesions must	
have an Atopic Dermatitis Severity Index (ADSI) ≥ 6 . The two site	2S
need to be comparable anatomically symmetrical sites. It will be in	n
the opinion of the Investigator based on subject's medical history	
whether the lesions are clinically stable.	
5. Female subjects of child-bearing potential must use at least one	
method of birth control that results in a low failure rate (i.e., less	
than 1% per year) when used consistently and correctly such as	
implants, injectables, combined oral contraceptives,	
some intrauterine devices (IUDs), sexual abstinence or	
vasectomized partner for the duration of study participation.	
6. Technical ability and willingness to self-apply, or LAR to apply,	
test articles during telemed visits with the study staff and	
unsupervised on weekends.	
7. Willingness to discontinue use of systemic AD treatments and	
topical treatments to the target areas for the duration of the study	
unless specifically permitted by the Investigator.	
8. Willingness to comply with test site restriction for 12 hours prior t	to
all office visits including the Baseline visit and for 12 hours after	er
each treatment application. These treatment site restrictions include	e:
a No washing of test sites with any cleansers or soaps at an	iv
time from the Baseline visit to completion of the Day 4	12
Follow up Visit Water passing over the areas durin	ι σ
showering is acceptable	.9
b No rubbing the test sites with a washcloth towel luffas P	at
dry after showering is acceptable	av
c No recreational activities in chlorinated or chemically treate	be
water such as swimming pools hot tubs and spas	/u
d No tight or form fitting clothing covering the treatment area	S
e No suphathing or use of suntan parlors or tanning beds	5.
f If participating in physical activities resulting in heav	N
nerspiration only not dry test site grass with towal if neede	y d
α Any activity that in the opinion of the investigator might alt	u. or
the quality of the samples collected or risk removal of the	л р
test article	IC.

	9. Willingness to undergo the following washout periods:
	a. Washout of 2 weeks prior to the Baseline visit for topical
	treatments used on the two treatment target sites, including
	but not limited to: antibacterial products, anti-
	inflammatories (e.g., corticosteroids, tacrolimus,
	Pimecrolimus). Other than the two treatment sites, topical
	medications may be used before/during the duration of the
	study. Subjects will be provided 1% hydrocortisone for
	treating non-target areas during the trial.
	b. Washout of 4 weeks prior to the Baseline visit for systemic
	treatments for AD, including but not limited to
	corticosteroids (oral or intramuscular injections), systemic
	immunomodulators or immunosuppressive agents (e.g.,
	methotrexate, cyclosporine, hydroxychloroquine).
	antibiotics (oral or injected, if required to treat a medical
	condition short duration of oral antibiotics (<10 days) are
	permitted after randomization)
	c Washout of 2 weeks prior to the Baseline visit for bleach
	haths
	d Washout of 2 weeks prior to the Baseline visit for
	nhototherany
	10 No history of allergy to at least two of the following classes of
	antibiotics.
	Cephalosporins Quinolones Tetracyclines Aminoglycosides
	Macrolides Carbapenems and Lipopentides
	11. Willingness to allow digital photos of treatment areas to be taken
	and stored.
Exclusion	1. Women who are pregnant, planning a pregnancy, breastfeeding or
Criteria	have a positive pregnancy test at screening.
	2. Any dermatological conditions that could interfere with clinical
	evaluations or any disease state or physical condition which might
	expose the subject to an unacceptable risk by study participation.
	3. Any underlying disease(s) or other dermatological conditions that
	require the use of exclusionary topical or systemic therapy.
	4. Spontaneously improving or rapidly deteriorating dermatitis
	anywhere on the body
	5 Netherton's syndrome or other genetic dermatoses that result in
	defective enidermal barrier function
	6 Treatment of any type of cancer within the last 6 months other than
	cutaneous basal cell carcinoma
	7 History of any significant internal disease (which contraindicates
	use of live microhiome e σ leukemia liver failure cardiovascular
	disease)
	8 Subjects who are known to be allergic to any of the test product(s)
	or any components in the test product(s) or history of

	hypersensitivity or allergic reactions to any of the study
	preparations as described in the Investigator's Brochure.
	9. AIDS or AIDS related complex by medical history.
	10. Known or suspected immune suppressive medications or diseases
	or any condition that in the opinion of the investigator would
	increase the subject's susceptibility to opportunistic infections.
	 Treatment with systemic immune modulating or anti-inflammatory biologic agents within 16 weeks of Baseline Visit.
	12. Poorly controlled diabetes mellitus Type I or II by medical history.
	13. Peripheral vascular disease based on medical history.
	14. Any subject not able to meet the study attendance and telemed visit requirements.
	15 Participants with a history of neurophistric disease or history of
	alcohol or drug abuse that would interfere with the ability to
	comply with the study protocol.
	16. Subjects who have participated in any other trial of an
	investigational drug or device within 30 days prior to enrollment or
	participation in a research study concurrent with this study.
Test sure des et	The first entities will be equilible by designed a could ded for the
lest product,	The test articles will be applied by designated unblinded treating investigator(g) at respective the investigational site(g) on $Pagaline/Day 1$
dose and mode	investigator(s) at respective the investigational site(s) on Baseline/Day 1 followed by weakly applications on Days $7(\pm/2)$, $14(\pm/2)$, and $21(\pm/2)$)
01 administration	The daily applications between visits will be applied by the subjects or
aummistr ation	LAR under the supervision of a designated treating investigator(s) or
	delegate(s), during a telemed visit on weekdays and unsupervised on
	weekends.
	Approximately 0.1ml of the assigned test articles will be applied to
	designated treatment sites.
	1mL vial of DBI-001 gel contains 10 ⁷ -10 ⁹ CFU/mL of
	Approximately 0.1mL applied to a treatment area that is approximately 100
	cm^2 will contain approximately 10^{4-6} CFU per cm^2 of
	Approximately 56 days (+/-4) including up to 14 days from Screening
Duration of	Visit to Baseline Visit, a 28 $(+/-2)$ day treatment period followed by a 14
Trial	(+/-4) day post treatment follow up.
Statistical	All subjects who are randomized and treated with test article will be
methods	included in the Intent-to-Treat analysis set.
	All subjects who are randomized, receive at least one (1) confirmed dose
	of test article, and have at least one (1) post-baseline safety assessment
	will be included in the Safety analysis set.

	The evaluation of S. aureus qPCR and CFU abundance will be performed on all subjects and separately in a modified intent to treat (MITT) population defined as subjects with bilateral abundant S. aureus at baseline as detected by qPCR. A MITT population defined as all subjects with detected by qPCR at one or more time points in samples obtained from one treatment targeted site but no detected in any sample from the contralateral treatment targeted site at any time point during the trial will also be evaluated.
	Linear interpolation of efficacy variables will be performed using observed data that precedes and follows the off-schedule visit, if present. The last observation will be carried forward if all the data subsequent to the off- schedule value is missing.
	No adjustments for multiplicity will be made; p-values are primarily presented for descriptive purposes.
Safety Evaluation	Tolerability will be evaluated through assessment of the severity of the signs and symptoms of the disease state (erythema, pruritus, exudation, excoriation and lichenification) as well as pain, burning, or stinging and review of adverse events. Any local skin reaction that requires use of a concomitant therapy or study discontinuation should be reported as an AE on the Case Report Forms (CRFs).
Sample Size	Sample size is based on clinical judgement and published literature on this type of trial and is deemed adequate to successfully demonstrate the stated goals.

Study Endpoints	 Primary Study Endpoint: The hypothesis of this trial related to clinical effect is that 4 weeks of daily dosing with DBI-001 will improve AD based on evaluation of signs and symptoms of AD in the comparison of sites treated with DBI-001 DP or Aqueous Gel on the following: Change from baseline in ADSI score at days 7 (±2), 14 (±2), 21 (±2), 28 (±2), 35 (±4) and 42 (±2). Change from baseline in individual signs and symptoms of AD (components of ADSI score) at days, 7 (±2), 14 (±2), 21 (±2), 28 (±2), 35 (±4) and 42 (±2).
	Secondary Endpoints:
	In the S. aureus MITT population, comparison of sites treated with DBI-001 or Aqueous Gel on the following microbial metrics:
	 Change from baseline in signs and symptoms of local tolerability (erythema, pruritus, exudation, excoriation and lichenification as well as pain, burning or stinging) for the DBI-001-treated sites vs. the Aqueous Gel-treated sites. Change from baseline in abundance of S. aureus based on molecular diagnostic qPCR on samples obtained from lesioned skin at days 7, 14, 21, 28, 35 and 42. Change from baseline in abundance of S. aureus based on CFU counts on samples obtained from lesioned skin at days 7, 14, 21, 28, 35 and 42. The proportion of subjects with a greater decrease in ADSI for the DBI-001-treated site than the Aqueous Gel-treated site. Changes in the abundance and diversity of the microbiome for the DBI-001-treated sites vs. the Aqueous Gel-treated sites. Mathematical sites vs. the Aqueous Gel-treated sites. Mathematical sites vs. the Aqueous Gel-treated sites.

Analysis of Efficacy	Primary:
	The primary analysis will compare the differences from baseline in ADSI score between DBI-001 and Aqueous Gel treated sites will be done using a two-sided Wilcoxon sign rank test at each of Days 7, 14, 21, 28, 35 and 42.
	The proportion of subjects with a greater decrease in ADSI for the DBI-001-treated sites than the Aqueous Gel-treated sites will be summarized descriptively for Days, 7, 14, 21, 28, 35, and 42.
	Comparison of differences at Day 28 between DBI-001 and Aqueous Gel of abundance of on treated sites will be done using a two-sided Wilcoxon sign rank test.
	Comparison of differences at Day 28 between DBI-001 and Aqueous Gel of abundance and diversity of the microbiome based on DNA sequencing will be done using a two-sided Wilcoxon sign rank test.
	Comparisons at Days 7, 14, 21, 35, and 42 will also be done.
	Additionally, a repeated measures model will be used to compare DBI-001 to Aqueous Gel for the secondary endpoints. P-values will be provided for descriptive purposes.
	Secondary: The secondary analysis of the S. aureus MITT population will compare the differences in change from baseline and Day 28 between DBI-001 and Aqueous Gel treated sites in abundance of S. aureus based on qPCR and CFU counts using a 2-sided Wilcoxon sign rank test, alpha = 0.05, with a null hypothesis of median difference equal to zero.
	Comparisons at Days 7, 14, 21, 35, and 42 will also be done.
	Additionally, a repeated measures model will be used to compare DBI-001 to Aqueous Gel for the secondary endpoint. P-values will be provided for descriptive purposes.
	Exploratory: Comparison in changes in the overall microbiome as defined by 16s and/or whole genome sequencing of samples obtained prior to, during, and after treatment.

	Comparison of change from baseline in individual signs and symptoms of AD (components of ADSI score) between DBI-001 and Aqueous Gel treated sites will be done using a two-sided sign test at each of Days 7, 14, 21, 28, 35, and 42.
	Additionally, a repeated measures model will be used to compare DBI-001 Gel to Aqueous Gel for the above exploratory endpoints.
Analysis of Safety	Signs and symptoms of local tolerability (erythema, pruritus, exudation, excoriation and lichenification as well as pain, burning, or stinging) will be summarized with changes from baseline.
	Subjects will be assessed for the occurrence of new and ongoing AEs. Descriptions of AEs will include the dates of onset and resolution (if resolved), maximum severity, seriousness, action taken regarding the investigational product, corrective treatment, outcome, and Investigator's assessment of causality. All reported treatment-emergent AEs (TEAEs), defined as any AE with an onset on or after the date of first investigational product application, will be summarized by treatment group, the number of subjects reporting TEAEs, system organ class, preferred term, severity, and relationship to investigational product. When summarizing TEAEs by severity or relationship to investigational product, each subject will be counted only once within a system organ class or a preferred term using the event with the greatest severity or causality, respectively, within each category. All reported serious adverse events (SAEs) will be summarized by treatment group, the number of subjects reporting SAEs, system organ class, preferred term, severity and relationship to investigational product.
	All information pertaining to AEs noted during the study will be listed by subject and will include a verbatim description of the event as reported by the Investigator, as well as the preferred term, system organ class, start date, stop date (if stopped), seriousness, severity, action taken regarding the investigational product, corrective treatment, outcome and relationship to the investigational product. In addition, a listing of subjects who prematurely discontinue from the study due to AEs will be provided as well as a listing of subjects who reported an SAE.
Adverse Events	During the study, subjects will be assessed for the occurrence of new and ongoing AEs. Descriptions of AEs will include the dates of onset and resolution (if resolved), maximum severity, and seriousness, corrective treatment, outcome, and the Investigator's assessment of causality. AEs present at any visit will be followed to resolution (return to normal or to the baseline state) or until clinically stable as determined by the Investigator.

Study Design/Type	This is a randomized, observer blinded, Aqueous Gel-controlled, daily application for 4 weeks, within-subject, bilateral comparison trial examining the effect of DBI-001 Gel vs. Aqueous Gel on the clinical ADSI scores and the abundance of S. aureus of comparable bilateral target sites of AD as well as signs and symptoms of local tolerability on treated sites in subjects.
	Subjects meeting the inclusion/exclusion criteria and having moderate to severe AD lesions at screening and baseline/Day 1 will be enrolled into the study.
	In an observer-blinded fashion, each subject will have two sites randomly assigned to have either DBI-001Gel or Aqueous Gel applied to the designated treatment targeted sites.
	After Screening, Study visits will occur at Day 1 Baseline then Days 7 (± 2), 14 (± 2), 21 (± 2), 28 (± 2), 35 (± 4), and 42 (± 4).
	At each study visit, the following procedures will be conducted: clinical assessment of signs and symptoms of AD, ADSI clinical scoring, clinical signs and symptoms of erythema, pruritus, exudation, excoriation, lichenification. pain, burning, or stinging, and collection of microbiologic samples. Photos of both treatment sites will be taken on all visits except the Screening Visit.

Table 1.Schedule of Events.

Evaluation	^a Screen (- 14 Day to day 0)	Day 1 Baseline	Day 7 (±2)	Day 14 (±2)	Day 21 (±2)	Day 28 (±2)	Day 35 (±2)	Day 42 (±4)
		•	Trea	tment	•	•	Fol	low-up
Demographics	X							
Inclusion/Exclusion	X							
Urine Pregnancy test (For Women of childbearing potential)	X			X				Х
Confirm Compliance with Treatment Site Restrictions ^b		Х	Х	Х	Х	Х	Х	Х
Medical History	X							
Concomitant Medication Query	Х	Х	Х	Х	х	Х	Х	Х
Adverse Events	X	X	Х	Х	Х	Х	Х	Х
Clinical Assessment of Local Tolerability		Xc	Х	X	X	X	X	X
Calculate ADSI Scores based on Signs and Symptoms of AD	x	x	X	Х	X	X	X	X
Digital Images of Both Treatment Sites		X	X	Х	X	X	X	X
PBS Swabs from both Sites		Х	Х	Х	Х	Х	Х	Х
Sample both Sites		X				X		
Apply Test Articles After all Evaluations and Sampling		X	X	Х	X			
Collect Returned Used and Unused Test Articles			Х	Х	Х	Х		
Dispense Test Articles for Home Application		Х	х	Х	х			
Review Treatment Site Restrictions		X	X	Х	X			
Review Procedures for Telemed Visits		X						
Dispense 1% Hydrocortisone Ointment as Needed		Х	x	Х	x	X	X	X
Appointment for Next Clinic Visit and Telemed ^a Visits	X ^a	X	Х	X	X	Х	X	

^a Screening and Baseline visits can be on the same day only if *all* eligibility criteria are met and *all* required Screening and Day 1/Baseline tests and tasks are completed on the same day.

^b Except for the Day 28, 35, or 42 visits, if violations of treatment site restrictions prior to the visit are reported, details of the violation should be recorded in the CRF and the visit should be completed including evaluations and sampling.

^c On Baseline/Day 1, local tolerability is to be assessed 30-minutes after application of test articles.

For the Day 28, 35, and 42 Visits:

If violations of treatment site restrictions reported occurred more than 24 hours prior to the visit at the Day 28, 35, or 42 visits, details of the violation should be recorded in the CRF and the evaluations and sampling completed as scheduled.

If violations of treatment site restrictions less than 24 hours prior to the visit is reported at the Day 28, 35, or 42 visits, details of the violation should be recorded in the CRF. Evaluations can be completed but an additional visit 24-48 hours after the violation should be scheduled for sample collections.

Details on sampling sites are in Table 2 and the Collection Sampling, Storage, Shipping Procedure, provided separately.

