3. STUDY OBJECTIVES AND PURPOSE

The purpose of the study is to evaluate the effect of 27 daily applications of DBI-001 on the signs and symptoms of active AD, and the safety and tolerability of DBI-001 in subjects with active AD. Secondly, to see the effect of this treatment on the abundance of *S. aureus*. Thirdly to evaluate the presence or persistence of \swarrow and the impact on the overall microbiome following once daily application of DBI-001 for 4 weeks.

STUDY DESIGN AND ENDPOINTS

Description of the Study Design

This is a randomized, observer blinded, Aqueous Gel-controlled, once daily application for 27 days within-subject, bilateral comparison trial examining the effect of DBI-001 Gel vs. Aqueous Gel. Approximately 20 subjects will be enrolled. Women of childbearing potential will be tested for pregnancy with urine pregnancy test. Women who are pregnant or who have a positive pregnancy test will be excluded from the study. At each investigative site there will be two types of investigators: treating investigators and evaluating or observing investigators. The treating investigator(s), or delegate(s), will apply the treatments and be unblinded to treatment assignment.

DermBiont

The observing or evaluating investigator(s) will be blinded to treatment assignment and perform all clinical evaluations.

Subjects meeting the inclusion/exclusion criteria will be enrolled into the study. Each subject's comparable anatomically symmetrical, bilateral treatment sites will be randomly assigned to be treated with either DBI-001 or the Aqueous Gel control. Treatments will be applied in the clinic by a treating investigator, or designee. On weekdays at home, the subjects, or LAR, will apply under the supervision (by telemed) of a treating investigator, or delegate(s), and unsupervised (no telemed visit) on weekends. Clinical evaluations will be made by a blinded-to-treatment evaluating investigator who will grade the severity of signs and symptoms of AD (erythema, pruritus, exudation, excoriation and lichenification) to calculate the ADSI score and local tolerability, which will also include assessment of the severity of pain, burning, or stinging as reported by subjects. Samples for microbiology will be tested by qPCR for the presence and abundance of and *S. aureus*, 16s and/or whole genome sequencing will be used to characterize the entire microbiome.

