4.2.2 Secondary Endpoints

In the *S. aureus* MITT population, comparison of sites treated with DBI-001 or Aqueous Gel on the following microbial metrics:

- Change from baseline in abundance of *S. aureus* based on molecular diagnostic qPCR and CFU counts on samples obtained from treatment sites at days 7, 14, 21, 28, 35, and 42.
- Abundance of based on qPCR and CFU counts.
- Changes in the abundance and diversity of the microbiome as determined by 16s and/or whole genome sequencing.
- The proportion of subjects with a greater decrease in ADSI for the DBI-001-treated site than the Aqueous Gel-treated site.
- Change from baseline in signs and symptoms of local tolerability (pruritus, erythema, exudation, excoriation, and lichenification as well as pain, burning, or stinging) for the DBI-001-treated lesion and the Aqueous Gel-treated lesion.

INVESTIGATIONAL PRODUCT (IP)

Investigational Product and Aqueous Gel (Test Articles)

Test articles	Doses per Subject
1mL vial contains DBI-001 Gel with 10 ⁷ -10 ⁹ CFU / mL of	27 doses (once daily for 4 weeks)

ELIGIBILTY CRITERIA

Inclusion Criteria

Subjects must meet all of the following criteria to be included in the study:

1. Ability to understand, agree to, and sign the study Informed Consent. If the subject is unable to provide consent for him/herself, the subject's legally authorized representative may provide written consent.

2. A signed Health Information Portability and Accountability Act (HIPAA) authorization form which permits the use and disclosure of subject's individually identifiable health information.

3. Male or Female Subjects of any race 12-65 years of age.

4. Physician diagnosed clinically stable AD according to the criteria of Hanifin and Rajka with comparable anatomically symmetrical, bilateral target lesions (Hanifin and Rajka 1980). Each lesion must have an Atopic Dermatitis Severity Index (ADSI) score of ≥ 6 . It will be in the

opinion of the Investigator based on subject's medical history whether the lesions are clinically stable.

5. Female subjects of child-bearing potential must use at least one method of birth control that results in a low failure rate (i.e., less than 3 % per year) when used consistently and correctly such as implants, injectables, combined oral contraceptives, some intrauterine devices (IUDs), sexual abstinence or vasectomized partner for the duration of study participation.

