6.5.2 All Other Visits

Study visit assessments and sample collections will be conducted as presented in Tables 2 and 3.

The Screening and Day 1/Baseline visit can be combined for subjects meeting *all* eligibility requirements and only if *all* Screening and Day 1/Baseline tests and tasks can be completed on the same day.

Day 1/Baseline visit:

- 1. Confirm compliance with treatment site restrictions.
- 2. Record any changes in concomitant medications.
- 3. Record adverse event, if any.
- 4. Blinded evaluating investigator complete clinical assessment of severity of signs and symptoms of AD prior to application of test article.
- 5. Calculate ADSI score of both potential treatment sites if the Screening visit was on an earlier date. At Baseline, if ADSI eligibility criterion is no longer met, the subject is to be withdrawn from the study prior to sample collection and test article application.
- 6. Digital images of both treatment sites.
- 7. Collect PBS swabs from both treatment sites.
- 8. Collect samples from both treatment sites.
- 9. Unblinded treating investigator, or designee, to train subjects and/or LAR on method for selfor LAR to apply with a training vial.
- 10. Unblinded treating investigator, or designee, apply test articles after all evaluations and sampling have been completed.
- 11. Blinded evaluating investigator complete clinical assessment of local tolerability (severity pain, burning, or stinging in addition to pruritus, erythema, exudation, excoriation, and lichenification) 30-minutes after application of test articles to both treatment sites.
- 12. Review treatment site restrictions.
- 13. Review procedures for telemed visits.
- 14. Dispense 1% hydrocortisone ointment as needed.
- 15. Schedule appointment for Day 7 clinic visit and telemed visits.

Detailed instructions for sample collection, storage, and shipping are in the Collection Sampling, Storage, Shipping Procedure (CSSSP) provided separately. If violations of treatment site restrictions prior to the visit are reported details of the violation should be recorded in the CRF and the visit should be completed including evaluations and sampling.

DermBiont

Day 7 (±2)

- 1. Confirm compliance with treatment site restrictions.
- 2. Record any changes in concomitant medications.
- 3. Record adverse event, if any.
- 4. Blinded evaluating investigator complete clinical assessment of severity of signs and symptoms of AD.

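### Pain, burning or stinging is never rated separately before the first dose, so its planned change from baseline can only be measured from a score taken 30 minutes after application

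*Combined protocol and SAP*

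**What the plan says.** In Table 1 the row "Clinical Assessment of Local Tolerability" has no mark at Screening. Its Day 1 mark carries footnote c: "On Baseline/Day 1, local tolerability is to be assessed 30-minutes after application of test articles". The Day 1 list in 6.5.2 agrees. Item 10 is the application, and item 11 has the blinded evaluator rate "local tolerability (severity pain, burning, or stinging in addition to pruritus, erythema, exudation, excoriation, and lichenification) 30-minutes after application of test articles".

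The pre-dose clinical rating is item 4: "Blinded evaluating investigator complete clinical assessment of severity of signs and symptoms of AD prior to application of test article". The Description of the Study Design shows what those signs and symptoms are: the evaluator is to "grade the severity of signs and symptoms of AD (erythema, pruritus, exudation, excoriation and lichenification) to calculate the ADSI score". Section 6.6.1 lists the same five components. Pain, burning or stinging is not one of them; 6.6.2 treats it as an additional tolerability symptom.

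Section 6.6.2 scores the item 0 to 3 by the worst intensity the subject reports. The recall period is 24 hours at Baseline and the time since the last visit afterwards.

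Section 4.2.2 lists as a secondary endpoint "Change from baseline in signs and symptoms of local tolerability (pruritus, erythema, exudation, excoriation, and lichenification as well as pain, burning, or stinging". The Synopsis makes it a comparison between sides: "as well as pain, burning or stinging) for the DBI-001-treated sites vs. the Aqueous Gel-treated sites". Section 7.3.1 plans summaries of changes from baseline. No section says which score is the baseline.

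**The concern.** A change from baseline for a tolerability symptom needs a score from before exposure. For pain, burning or stinging none is scheduled, so the analyst would have to use the 30-minute score, which already contains any immediate reaction to the product.

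Tolerability of DBI-001 Gel against Aqueous Gel is a secondary objective. If DBI-001 stings on first use, that reaction is subtracted from every later DBI-001 score. Stinging that recurs during treatment can then appear as no change. Stinging that stops can appear as improvement at Days 35 and 42, when nothing has been applied since the previous visit. In both cases the error favours the product that caused the reaction.

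**Working it through.** **Is there a pre-dose score?**

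| Occasion | What is rated | Pain, burning or stinging? |
|---|---|---|
| Screening (6.5.1 item 8; Table 1) | AD signs and symptoms, ADSI | No |
| Day 1 before application (6.5.2 item 4) | AD signs and symptoms | No |
| Day 1, 30 minutes after application (6.5.2 item 11; Table 1 footnote c) | Local tolerability | Yes |
| Days 7, 14, 21, 28, 35, 42 | Both | Yes |

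Scheduled pre-dose ratings of this item: 0. Day 1 ratings: 1, after the dose.

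**What the 30-minute score contains.** Let B be the worst pre-dose score in the recall window and R the worst score in the 30 minutes after application, each 0 to 3. A 24-hour recall taken at 30 minutes covers about 23.5 hours before the dose and 0.5 hour after it. The recorded value is max(B, R), which cannot be split afterwards. Of the 16 possible (B, R) pairs, 6 have R above B; the documents do not say how likely each pair is.

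**Effect on the change score.** For a later score S:

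- planned change = S − max(B, R)
- change from a pre-dose value = S − B
- difference = −max(R − B, 0)

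S drops out, so the difference is the same at all six later visits. It also does not depend on what happens at other sites. With 20 subjects, the shift in a side's mean change is −(sum of max(R − B, 0) over affected sites)/20. Per affected site this is 1/20 = 0.05, 2/20 = 0.10 or 3/20 = 0.15 points too low.

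**Illustration (assumed: 5 of 20 DBI-001 sites react, no gel site does).** Mean change is too low by 5 × max(R − B, 0)/20:

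| | R = 1 | R = 2 | R = 3 |
|---|---|---|---|
| B = 0 | 0.25 | 0.50 | 0.75 |
| B = 1 | 0 | 0.25 | 0.50 |
| B = 2 | 0 | 0 | 0.25 |
| B = 3 | 0 | 0 | 0 |

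**Comparison between sides.** With R = 2 and B = 0 at 5 DBI-001 sites and at g gel sites, the error is (10 − 2g)/20: 0.50 for g = 0, 0.30 for g = 2 and 0 for g = 5.

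**How it would look over time** (R = 2, B = 0 at 5 DBI-001 sites, no change at the other 15):

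- Reaction recurs at score 2 at Days 7 to 28: planned mean change 5 × (2 − 2)/20 = 0, against 5 × (2 − 0)/20 = +0.50 from a pre-dose value.
- Score back to 0 at Days 35 and 42: planned 5 × (0 − 2)/20 = −0.50, against 0.

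**The case against.** - **The 24-hour recall reaches back before the dose.** It does, and where B is at least R the recorded value equals the pre-dose value. The exact statement is therefore that no separate pre-dose value exists. That does not help where R exceeds B.
- **The passages may simply be inconsistent.** Table 1 also has the row "Apply Test Articles After all Evaluations and Sampling", marked on Day 1, and item 10 says much the same, yet item 11 is an evaluation after application. The Description of the Study Design and 6.6.1 also mention recording this symptom, without timing. This makes the intention unclear, but none of these passages schedules a pre-dose rating, and the two that give a time agree on 30 minutes after.
- **Little stinging may occur.** Section 1.2 reports that a single application was well tolerated in the earlier AD trial. Lesions must score at least 6 on ADSI, so B = 0 cannot be taken as typical. Both points stand: the size is unknown and the one-sided example is only an illustration.
- **A pre-dose baseline is not like-for-like either.** It compares a one-day worst with roughly a one-week worst. True; that is a separate mismatch which the fix leaves in place.
- **The consequences are limited.** The summary is descriptive, raw scores can be compared side to side at each visit, and adverse events are collected from the first application. This limits the harm, though Other Required Safety Assessments ties AE recording partly to worsening from Baseline, so an inflated Baseline could weaken that route.
- **The separate SAP can define baseline.** It can, but it cannot supply a score that was not collected.

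**Conclusion.** The concern holds. Followed exactly, the protocol leaves a listed secondary endpoint with no separate pre-dose value for pain, burning or stinging, and any first-dose reaction above the pre-dose level enters the only available baseline. The understatement is 0.05 to 0.15 points in a side's mean change per affected site, assuming 20 evaluable subjects and that the subject reports the true worst intensity over the window. The total depends on an unknown number of affected sites, is zero where B is at least R, and cancels between sides when the excess is equal. The ADSI endpoint is untouched. This should be fixed before Day 1 data are collected, because the missing score cannot be recovered later.

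A smaller related point: the five AD items are rated both before application (item 4) and at 30 minutes (item 11), and the protocol does not say which is their tolerability baseline. That needs only a definition.

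**What to change.** - Add a 0-3 pain, burning or stinging rating for each site to the pre-dose Day 1 assessment (6.5.2 item 4), and name it in 7.3.1 as the baseline for that item. Item 4 also precedes swabbing, so irritation from the PBS solution, which Potential Risks mentions, stays out of the baseline too.
- Keep the 30-minute rating, word the question as since application, and report it as the first post-dose time point.
- Bring Table 1 footnote c, the Table 1 application row, Day 1 item 10 and 6.6.2 into line with this.
- Name the existing item 4 scores as the tolerability baseline for the five AD items.

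The cost is one extra 0-3 question per site on Day 1 and the matching CRF entry, with no extra visit, staff or procedure. For any subject already past Day 1, treat the 30-minute score as a post-dose value and compare the two sides on raw scores.
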